5.1 Inclusion Criteria

In order to be eligible to participate in this study, an individual must meet all the following criteria:

1. 30-80 years of age of any gender and;
2. Kellgren-Lawrence Grade 2, 3, or 4 (in select subjects who have no bony deformity)* knee OA on most recent knee radiograph obtained within 6 months of screening visit and;
3. Knee pain resistant to conservative treatment for at least 3 months* (anti-inflammatory drugs, acetaminophen, physical therapy, muscle strengthening, or intra-articular injection of hyaluronic acid and/or steroids); and
4. Moderate to severe knee pain: pain VAS ≥ 40 mm with 0 representing 'no pain' and 100 'the worst pain imaginable'. If both knees meet inclusion criteria, the one with a higher VAS score will be chosen for the study (i.e., target knee).
5. Willing, able, and mentally competent to provide informed consent and complete study questionnaires in English. The Study questionnaire is validated in English.

A recent study by Padio S et al included subjects with KL grade 4 and published results showed, similar to other studies, clinical reduction in pain score with no added risks. The scientific rationale for adding these subjects with KL grade 4 (severe knee OA with no bone deformity) is based on recent literature data (Citation: JB JS Open Access. 2021 Oct-Dec; 6(4): e21.00085.)

*3 months was chosen because this time interval is thought adequate for knee pain to be considered refractory to conservative care.

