
1- If not previously available (i.e., recent knee MRI within 3 months of screening); if MRI cannot be obtained on the same day due to subject preference and/or MRI scheduling related reasons, MRI can be performed anytime between the baseline visit and intervention visit
 
2- If not previously available (i.e., recent knee radiograph within 6 months of screening). Can be performed on a separate day based on appointment availability or subject's preference.
 
3- Post-procedural MRI can be done on a separate day of visit 6 based on appointment availability and subject's preference as long as it's performed within the timeframe of 3month +/- 10 days.
 
* Visit 1 and 2 can be combined based on subject preference. In that case, procedures listed in visit 2 will be performed after signing informed consent on the same day.
 
** Visit 4 (1-day follow-up) dates range can be +3 days (phone call, telemedicine, or in-person IR clinic visit determined by subject's preference and need for physical examination)
 
*** Visit 8. Optional visit for participants who completed 12 month follow up by August 31, 2024 (by invitation, voluntary, and after obtaining informed consent for this visit). This visit can be performed at any time interval within 18 months – 48 months
								

CONFIDENTIAL

post procedure. This visit can be performed by sending the questionnaire by a safe email and participants can email it back to research coordinator or PI OR by a phone call performed by research coordinator,
	
# 1, 3, 12-month follow-up dates range can be +/- 10 days
	
## The pre-procedural blood work can be done on the day of the procedure prior to performing the procedure based on subject's preference.
	
--	--	--	--

1 Key Roles

- **Principal Investigator (PI):** Will be one of two interventional radiologists performing the procedure. Will be responsible for study integrity, data monitoring, data collection, statistical analysis, and manuscript writing.

[name]

Clinical Assistant Professor of Radiology
Director, Vascular and Interventional Radiology Research Program
Department of Radiology, NYU Langone Health
[name]
[contact]
Email: [contact]

- **Co-PI:** Co-investigator involved in recruiting patients and conducting the clinical assessment for knee osteoarthritis

[name]

Associate Professor
Department of Internal Medicine, NYU Langone Orthopedic Center
[name]

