4.1 Description of Study Design

This study is a single-center, single arm, no sham or placebo, open label, prospective pilot study designed to evaluate the safety and feasibility of geniculate artery embolization for the treatment of knee OA. Enrolled patients will receive angiography and embolization of the one or more geniculate arteries in the affected knee using 250 µm Embosphere microspheres. If both knees are affected, the knee with the higher pain score on electronic VAS will be targeted.

The primary objective is to evaluate the effectiveness of geniculate artery embolization in reducing knee pain at 3 months. The primary objective will be evaluated by the clinical success rate. Clinical success is defined as at least 50% reduction in WOMAC pain score at 3-month follow up visit. 40 patients will be required for this study. The study would accrue 50 patients to account for an attrition rate of 20%.

Change in WOMAC pain score and pain VAS will be used as a measure of efficacy (i.e., pain reduction).

WOMAC questionnaire is a widely used, disease-specific measure for knee OA. It includes 24 questions on daily activities. WOMAC pain score includes five questions regarding pain (pain during walking, stair climbing, nocturnal, rest, weight bearing); each question will be scored using the

CONFIDENTIAL

following points: 0 for no pain, 1 for mild, 2 for moderate, 3 for severe, and 4 for extreme pain. possible score ranges for pain are 0–20. For this purpose, WOMAC Score will be calculated from the Knee injury and Osteoarthritis Outcome Score (KOOS) score which was developed as an extension of the WOMAC score with the purpose of evaluating short-term and long-term symptoms and function in subjects with knee injury and osteoarthritis. This means that the KOOS questionnaires will be administered to patients during visits and the WOMAC score will be calculated from the KOOS scores later at the time of data analysis.

The electronic VAS is a horizontal line with no markings on the scale except “No pain” on the left (score: 0 mm) and “worst possible pain” on the right end of the scale (score: 100 mm). Subjects mark the VAS to indicate their current pain level, with 0 mm representing “No pain” and 100 mm representing “worst possible pain”. In our study, subjects will be asked to mark their pain level on a paper VAS on study questionnaire form and will give a score between 0 to 100, which will be documented on the appropriate eCRF.

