7.3.2 Enrollment/Baseline (Visit 2, Day -29 to -1)- In interventional radiology clinic

- Verify informed consent of potential participant (study consent)
- Verify subject's eligibility
- Targeted physical exam
- Administration of study questionnaires
- Previous / concomitant treatments
- Baseline MRI (if one is not available within the last 3 months)
- Baseline knee radiograph (if one is not available within the last 6 months)
- Peripheral venous blood draws and urine sample (baseline laboratory tests)
- Note: Subjects will be required to withhold pain medications 24 hours prior to screening and each visit for the evaluation of pain

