10.4.3 Analysis of the Secondary Endpoint(s)

Analysis of secondary endpoints include: (1) changes in the mean WOMAC and VAS pain scores, the mean WOMAC knee stiffness and physical function scores and the total WOMAC knee physical function score; (2) the technical success rate (defined as the proportion of patients for whom the procedure was successfully completed); (3) the adverse event rate (defined as the proportion of patients showing each type of adverse event or any adverse event); (4) reduction in the usage of pain medication, the frequency of infection therapy, the need for physical therapy; and (5) the proportion of patients showing synovial thickening, joint effusion, meniscus tear, synovial enhancement, osteophytes. A point estimate and 95% confidence interval will be provided for each secondary outcome at each time and for the change in each outcome from baseline to each post-treatment follow-up visit. Changes in the outcomes from baseline to follow-up will be tested using the paired-sample Wilcoxon signed rank test for the WOMAC and VAS scores and the McNemar test for the other measures which will be assessed as binary outcomes (e.g., whether or not the patient reported usage of pain medication on a daily basis).

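### The VAS reading that appears to admit the patient and choose the knee is also the VAS baseline, so part of the VAS improvement is regression to the mean

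*Combined protocol and SAP*

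**What the plan says.** Section 5.1 sets the entry threshold, "Moderate to severe knee pain: pain VAS ≥ 40 mm", and the choice of knee, "If both knees meet inclusion criteria, the one with a higher VAS score will be chosen for the study". Section 4.1 repeats the second rule ("If both knees are affected, the knee with the higher pain score on electronic VAS will be targeted") and describes the scale as momentary: "Subjects mark the VAS to indicate their current pain level".

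The Schedule of Activities marks pain VAS and KOOS at Visit 2 (baseline) and at follow-up. The Visit 1 (screening) cells are blank. Section 7.3.1 lists no questionnaires at screening. Section 7.3.2 puts "Verify subject's eligibility" and "Administration of study questionnaires" in the same visit. A footnote to the schedule adds: "Visit 1 and 2 can be combined based on subject preference".

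Section 4.2.2 makes VAS at 1, 3 and 12 months a secondary efficacy endpoint, and Section 10.4.3 tests it within patient: "Changes in the outcomes from baseline to follow-up will be tested using the paired-sample Wilcoxon signed rank test for the WOMAC and VAS scores". Section 10.2 confirms that there is no comparison group. No repeat or averaged baseline is planned, and no adjustment for regression to the mean.

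**The concern.** A momentary pain mark is the patient's usual level plus that day's deviation. Patients admitted because the mark reached 40 mm, and knees chosen because they gave the larger of two marks, have on average a positive deviation at selection. A later reading has no such excess, so the mean falls with no treatment effect. A control arm would show the same fall and remove it; here nothing does.

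At stake is how the VAS change is read. The fall always favours the device. The planned test compares the change with zero, so it can declare an improvement that comes from the entry rule.

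**Working it through.** **The plan's own figure.** The plan gives no reliability or expected change for VAS. The one design figure this point touches is the 16-of-23 rule in Sections 10.2 and 10.5. The exact binomial gives P(X ≥ 16 | 23, 0.5) = 0.0466 and P(X ≥ 16 | 23, 0.75) = 0.8037. The stated 0.047 and 80.4% reproduce.

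**Step 1: threshold, one painful knee.** With true SD σt, day-to-day error SD σe, total SD σ = √(σt² + σe²) and a = (40 − mean)/σ, the expected fall with no treatment effect is (σe²/σ) × φ(a)/(1 − Φ(a)). All inputs except the 40 mm cut-off are assumptions: mean 50-60, σt 18-20, σe 10-15.
- Mean 60, σt 20, σe 10: σ = 22.36, a = −0.894; 4.472 × 0.2674/0.8145 = 1.5 mm.
- Mean 50, σt 18, σe 15: σ = 23.43, a = −0.427; 9.603 × 0.3642/0.6652 = 5.3 mm.

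**Step 2: add the higher-of-two-knees rule.** Simulation with 1,000,000 patients per scenario, scores clipped to 0-100, correlation 0.7 between the knees' true levels, independent errors and half the patients bilateral: about 3.0-7.4 mm. If a second independent reading is the baseline instead, the mean fall is about zero in every scenario.

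**Step 3: the cited cohort.** Section 2.2.2 cites a 20-patient study with baseline VAS 76 ± 14 mm. Use that as the pre-selection distribution, with assumed reliability 0.6.
- Threshold: a = (40 − 76)/14 = −2.571; fall = 0.4 × 14 × φ(a)/(1 − Φ(a)) = 0.08 mm, at most 0.1 mm by simulation.
- Knee choice, every patient bilateral: fall = σe²(1 − ρ)/s × √(2/π), where ρ is the correlation between the two knees' errors and s the SD of the difference between their readings. Here σe² = 0.4 × 196 = 78.4 and σt² = 117.6. With between-knee correlation 0.7, s² = 2 × 117.6 × 0.3 + 2 × 78.4 × (1 − ρ). For ρ = 0.5, s = 12.2 and the fall is 2.6 mm. For ρ = 0, s = 15.1 and the fall is 4.1 mm. The simulated upper figure was 2.9 mm. With half the patients bilateral these roughly halve.

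**Step 4: effect on the planned test.** Wilcoxon at N = 40, no treatment effect, assumed two-sided 5% level. False improvement was declared in roughly 9% of trials (60/18/10, one knee), a quarter (60/20/10, half bilateral), a third (50/20/15, one knee) and just over 60% (50/18/15, half bilateral). The nominal rate in that direction is 2.5%. Inputs are mean/σt/σe.

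**Step 5: WOMAC pain.** It is carried along only through the correlation r between its same-day error and the VAS error: WOMAC fall = r × (WOMAC error SD/VAS error SD) × VAS fall. Assume WOMAC pain mean 11 and SD 3.5, VAS SD 20, and equal reliability, so the ratio is 3.5/20 = 0.175.
- r = 0: no fall.
- VAS 60/20 (mean/total SD), reliability 0.75, half bilateral, r = 0.5: 0.5 × 0.175 × 2.36 = 0.21 points (simulated 0.208).
- VAS 50/20, reliability 0.6, half bilateral (VAS fall about 5 mm), r = 0.8: 0.8 × 0.175 × 5 = 0.7 of 20 points.

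Over this range a true 50% response reads as 50-54%. The false-success probability of the 16-of-23 rule is 6.8% at 52% and 9.8% at 54%, against 4.7% at 50%. With no treatment effect at all, 0.1-3.2% of patients show a 50% WOMAC fall by measurement noise.

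**The case against.** **The single reading is an inference.** Section 7.3.1 reviews eligibility at screening, and eligibility includes the VAS threshold. The analgesic note in Section 7.3.2 speaks of withholding before screening and each visit for the evaluation of pain. If a screening VAS is taken, the two readings are already separate when the visits are separate. This stands as a caution: the documents never say outright that one reading does all three jobs. But the schedule shows no VAS at Visit 1, and the visits may be combined, so the plan needs clarifying either way.

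**The primary endpoint.** A reader might infer that the 50% responder rate is inflated in the same way, because KOOS is completed at the same visit. The documents do not support that. There is no WOMAC entry threshold, no knee is chosen on WOMAC, and the five-item score has its own baseline. Only shared same-day error links it to the selection, and the documents give no figure for that.

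**Halving of VAS.** A reader might also count patients whose VAS halves by chance (1.2-9.2% in these scenarios) as a selection artefact. No endpoint is defined that way, and 0.7-5.8% would still halve with a separate baseline, so most of it is ordinary noise.

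**Size.** The plan's own anchors are high: 76 ± 14 mm, and a median of 8 of 10 in the study cited in Section 2.1. These are values after selection in other trials, so they do not settle the matter, but they make a negligible threshold effect plausible. The knee-choice effect remains.

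**Timing.** The trial is under way: Section 2.2 records an expansion by 21 patients, and Visit 8 is for those who completed 12 months by August 31, 2024. Treated patients cannot be given a new baseline. That stands and shapes the remedy.

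**Conclusion.** The point holds for VAS. As scheduled, the selecting reading appears to be the VAS baseline, and the uncontrolled change then contains regression to the mean that favours the device. The size rests on inputs that the documents do not give: about 1.5-7.4 mm for a population mean of 50-60 mm and error SD 10-15 mm. For patients like the cited 76 ± 14 mm cohort it is at most about 0.1 mm from the threshold plus about 3 mm from the knee choice (4 mm if every patient is bilateral and the knees' errors are independent).

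For WOMAC pain and the primary responder rate the effect is indirect and small, from zero to 0.7 of 20 points. It could raise the false-success rate modestly near a true 50% response. It cannot produce success by itself, because noise alone makes at most 3.2% of patients responders against a null of 50%. This is a bias in a secondary endpoint of an open-label pilot that is cheap to reduce; it does not invalidate the primary analysis.

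**What to change.** **Patients not yet treated.** Add a VAS for each knee at Visit 1 to the Schedule of Activities, used only for eligibility and knee choice. Take the analysis baseline VAS and KOOS for the chosen knee on a different day before the procedure: at Visit 2 when it is separate, otherwise on Day 0 before sedation. Do not re-apply the 40 mm cut-off to that second reading, since doing so would bring the selection back. State in Section 10.4 that changes are calculated from it.

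**Patients already treated.** State which reading served as baseline and whether one or both knees qualified. Add a sensitivity analysis that subtracts the expected fall from the VAS change over a range of assumed reliabilities, for example 0.6-0.9, with the threshold and knee-choice parts shown separately.

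**Cost.** One extra form per patient and a line in the schedule, with no new visit. The apparent VAS improvement will be slightly smaller. A change made mid-trial leaves two baseline definitions, which should be reported separately.

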5.2 Exclusion Criteria

An individual who meets any of the following criteria will be excluded from participation in this study:

1. Active systemic or local knee infection or;
2. Active malignancy or;
3. Life expectancy less than 12 months or;
4. Prior ipsilateral knee surgery (within 3 years of baseline visit), arthroscopic surgery (within 6 months of baseline), total or partial knee replacement regardless of timing or;
5. Ipsilateral knee intra-articular injection in the last 3 months or;
6. Rheumatoid arthritis, spondyloarthropathies, crystal disease, gout, pseudogout, or lupus;
7. Pregnant during the study period or;
8. Renal dysfunction as defined by serum creatinine > 1.6 dl/mg or eGFR < 60 on blood tests obtained within 30 days of procedure or;
9. Body weight greater than 200 Kg or;
10. Uncorrectable coagulopathy (platelet count $< 50,000$, international normalized ratio > 1.5 within 30 days of procedure; or
11. Known history of contrast allergy resulting in anaphylaxis or;
12. Known significant arterial atherosclerosis that would limit selective angiography and/or lower extremity symptoms thought to be secondary to arterial vascular disease (eg claudication, ischemic rest pain)
13. Post-traumatic knee (if trauma occurred within 12 months of baseline or was associated with fractures)
14. known avascular necrosis in the target knee
15. Contraindications to MRI such as such as claustrophobia, metallic fragment/implants, pacemaker.

CONFIDENTIAL

5.3 Vulnerable Subjects

The study does not intend to recruit vulnerable subjects. The study will not recruit any children, pregnant women, fetuses, neonates, or prisoners.

5.4 Strategies for Recruitment and Retention

Participants will be recruited at the study investigator or sub-investigator clinical practices (visit 1). A study investigator or sub-investigator will assess the medical record of potential subjects for eligibility and provide eligible participants with written information (i.e. study brochure) regarding the study during the initial study visit [attachment 6] and obtain informed consent.

IRB-approved study coordinator or co-investigator will guide interested people through written informed consent. knee X-rays will be graded with the Kellgren-Lawrence scale by a board certified, fellowship-trained musculoskeletal radiologist (Co-PI) [29]. Recruitment is expected to occur over 3 years. To achieve primary objective, data from 40 patients will be required and the study would accrue 50 patients to account for an attrition rate of 20%.

Only NYULH individuals who are listed on the NYU Langone Health IRB-approved protocol will approach patients for consent. A study brochure will be provided for potential subjects [attachment 6]. The study brochure will also be available in NYULH rheumatology, orthopedics, family medicine, and interventional radiology clinics and will be also disseminated on social media (e.g. Facebook, Twitter, blogging) to advertise for the study after IRB approval. The study brochure will include contact information for interested subjects to contact study coordinator and/or PI.

Once enrolled, IRB-approved study coordinator will notify and remind participants about the visits.

Participation in the study is voluntary; no financial incentives will be offered.

5.4.1 Use of DataCore/Epic Information for Recruitment Purposes

This study will utilize EPIC to identify subjects. DataCore will request a report after obtaining IRB approval. The report will be requested to generate a list of potential subjects with a diagnosis of knee OA and who meet eligibility criteria from the electronic medical system of NYULH.

The VIR / Radiology research coordinator, [name] (PI), [name] (co-PI), and [name] (co-PI) will have access to EPIC search results. The list will be filtered to identify patients who meet eligibility criteria listed in this protocol.

The PHIs that will be extracted from the EPIC search will be patient's name, MRN, contact information, and name and contact information of the treating physician (TP). The dataset will be deleted after discontinuation, termination, or completion of the study.

Queries regarding eligible subjects will run during the course of the study once a month until discontinuation, termination, or completion of the study.

Once potential subjects have been identified, the study team will notify the TP that they have patients eligible to participate as follow:

- Treating physician will be notified that the study team will contact potential subjects directly, by phone, email, or the MyChart portal.

CONFIDENTIAL

This material is the property of the NYU School of Medicine and Langone Medical Center. Do not disclose or use except as authorized in writing by the study sponsor
Interventional Template Version: 12 February 2020

- If TP agrees to permit study team to directly contact potential subjects on behalf of TP, a study coordinator or investigator will inform the potential subjects about the study using standard language [attachments 7&8] and study brochure [attachment 6].

Patients will be contacted by email, the MyChart portal, MyChart recruitment tools through DataCore, and/or direct phone call using standard language attached to this protocol [attachments 7 and 8]. When sending recruitment information by email, SendSafe Secure email will be used to contact patients.

Once contact is made, the IRB-approved study brochure or language included in the approved study brochure (if contact made by phone) will be used to communicate the reason they are being contacted and subjects will be asked if they are interested in participating in this specific study. Should the potential subjects agree, the study team will provide the subjects with information regarding the next steps for participation.

If a subject requests information regarding opting out of further recruitment for all research, subjects will be directed to contact the VIR research coordinator or the PI at [contact] or at the office number [contact]. The contact information is also be available on the study brochure. If patient agrees to participate, he will be scheduled for a clinic visit with one of the investigators (visit 1) to further discuss the study, complete the screening elements, and obtain informed consent.

If a subject requests information regarding opting out of further recruitment for all research, subjects will be directed to contact study coordinator or have subjects contact [contact] or [name].

5.5 Duration of Study Participation

Each subject will be enrolled in the study for approximately 13 months from the initial screening visit (visit 1; Day -30) until the last follow-up visit at 12 months post intervention (visit 7; Day 360).

